**Table 2: Oxfendazole Placebo Formulation and Packaging**

Item	Material	Amount % (w/v)
1	Polyethylene Glycol, NF	4.5%
2	Methyl Paraben, NF	0.18%
3	Sterile Water For Injection, USP	95.32%
4	22 mL Screw Thread Vial with 20/400 PTFE Lined Cap	N/A
Total		100.00

Corrugated box inserted with vials partition will be used to pack oxfendazole placebo vials.

Each vial has been affixed with a 2" x 4" open text label. The label text is described in Figure 1.

**Figure 1: Oxfendazole placebo label text description**

Oxfendazole Placebo, 15 mL	
Batch No.: 16146-10    Manufacture Date: Oct. 2013	
Store at temperature not exceeding 25°C (77°F)	
Caution: New Drug Limited by Federal (US) Law to Investigational Use Only. Keep out of the reach of children.	
Manufactured for the National Institute of Allergy and Infectious Disease (NIAID), Bethesda, MD 20817 by SRI International, Menlo Park, CA 94025	

### 5.1.3 Product Storage and Stability

Oxfendazole should be stored at room temperature (20°- 25° C) though excursions between 15° and 30°C for less than 24 hours are acceptable.

Oxfendazole placebo is recommended to store at temperatures not to exceed 77°F ( 25°C).

The stability of oxfendazole placebo is under evaluation. The stability study at 25°C/60% RH (testing at 3, 6, 9 and 12 months) and 40 °C/75% RH (testing at 3 and 6 months) has been initiated.

## 5.2 Dosage, Preparation and Administration of Study Intervention/Investigational Product

**Table 3. Schema for administration of Synanthic® available product strengths**

Dose ID	Synanthic®		Dosing protocol		
	Concentration of dosing suspension (mg/mL)	Source of dosing suspension	Protocol dose (mg/kg)	mL to be administered	Vol for 80 kg subject (mL)
A	90.6	9.06% Synanthic®	0.5	kg x 0.0055	0.44
B			1.0	kg x 0.011	0.88
C			3.0	kg x 0.033	2.65
D			7.5	kg x 0.083	6.62
E	225	22.5% Synanthic®	15	kg x 0.067	5.32
F			30	kg x 0.133	10.66
G			60	kg x 0.267	21.33

Note: Aliquots will be removed from the Synanthic® stock bottle immediately after mixing, as the marketed drug is a suspension. The content of the oral dosing syringe will be mixed in the pharmacy and transported to the clinical research for administration. Administration must occur within 20 minutes after mixing in the pharmacy. Immediately following administration of the dose, the subject will drink 100 mL of water to assure that the entire dose is taken. If the dose is not administered within 20 minutes it should be discarded and a fresh dose mixed in the pharmacy.

### **5.3 Modification of Study Intervention/Investigational Product for a Subject**

None as subjects will only receive a single dose.

### **5.4 Accountability Procedures for the Study Intervention/Investigational Product(s)**

The investigator will sign that he has received the study medication, confirming the quantity received and registering its characteristics, including lot number and expiration date. Upon arrival, the drug will be stored locked in the facilities of each study center at appropriate temperature. The Study Pharmacist (as delegated by the Principal Investigator) will be responsible for appropriate handling and storage of the study medication and ensuring that it is dispensed to study subjects only in accordance with the protocol. A new bottle of Synanthic® will be opened for use on each day of drug administration. A record will be maintained of all study medication dispensed to each subject. Drug suspension not used will be retained in the original containers.

The study products will be sent to the DMID central repository as directed by DHHS, and then will be supplied by the DMID central repository to the participating VTEU site prior to the start of the study.

After receipt of study products, the site principal investigator is responsible for their distribution and disposition, and has ultimate responsibility for study product accountability. Logs of receipt, temperature, maintenance, and disposal must be maintained in the study file. The study product accountability records and dispensing logs will also capture time of preparation of the diluted study drug. IDS staff will develop a master Compounding Record for each product to be prepared and will follow the Departmental SOP for Compounding Procedures during the product preparation.

Each item and volume/weight used in the preparation is double checked. At least one person involved in the process must be a pharmacist. All doses of study drug whether administered or not must be documented on the appropriate study product accountability record or dispensing

log. The sponsor's monitoring staff will verify the participating VTEU sites' study product accountability records and dispensing logs per the site monitoring plan.

Unused bottles of the study products will be retained until monitored and released for disposition as applicable. Final disposition of the unused study drug will be determined by DMID and communicated to the participating VTEU sites by the DMID Clinical Project Manager.

## **5.5 Assessment of Subject Compliance with Study Intervention/Investigational Product**

Oral intake of the study product by the subject will be observed by study personnel. Immediately following administration of the dose, the subject will drink 100 mL of water to assure the entire dose is taken. If vomiting occurs at any time following ingestion of the study product, no further dosing will be provided and subject will continue to be followed for safety and pharmacokinetic analyses. Subjects who have vomiting after administration of the dose will not be replaced.

## **5.6 Concomitant Medications/Treatments**

It is the goal of this study to enroll subjects who are healthy and on no chronic medications. Subjects will be counseled to refrain from taking prescription medications other than topical agents during the study period unless provided by an investigator or other licensed medical provider. Additionally, subjects will be counseled to avoid all over the counter medications unless absolutely necessary and will be asked to consult with a study investigator prior to use of over the counter medications. Subjects will be counseled to avoid acetaminophen since this medication can be associated with hepatotoxicity.

Administration of any medications, therapies, or vaccines will be recorded on the appropriate data collection form. Concomitant medications will include all current medications and medications taken within 30 days prior to signing the informed consent form through Day 15.. Prescription and over-the-counter drugs will be included as well as vitamins and supplements.

Use of new medication should prompt evaluation for the presence of a new diagnosis of chronic medical disease or chronic medical condition.

## 6 STUDY SCHEDULE (SEE APPENDIX A)

### 6.1 Screening (Day -28 to -1): Clinic Visit 01

*Informed Consent.* Written informed consent will be obtained prior to any other study procedures.

*History.* A complete medical history will be taken by a study nurse or study investigator. Emphasis will be placed on the absence of significant medical or psychiatric illness and the absence of recent illness and recent or current medication, except use of over the counter or prescription medications that are taken on average less than once per week.

*Physical Examination.*

- A routine physical examination will be performed by a study clinician licensed to make medical diagnoses.
- Height, weight, vital signs including oral temperature, blood pressure, and pulse will be obtained.

*Obtain 15 mL of blood for the following studies:*

- **Hematology:** Hemoglobin, white blood cell count with neutrophil and eosinophil counts, platelet count.
- **Chemistry:** Creatinine, alanine aminotransferase (ALT), aspartate aminotransferase (AST), random glucose and total bilirubin will be used as screening tests.
- **Serology:** Hepatitis B surface antigen, hepatitis C antibody, human immunodeficiency virus (HIV). If the subject tests positive for HIV or Hepatitis, they will be referred for medical follow-up and counseling.)

*Obtain urine sample for:*

- **Urine analysis:** Urine dipstick for protein and glucose

*EKG.* Perform electrocardiogram. EKG will be reviewed by a cardiologist.

Subjects that qualify for enrollment will be asked to agree to the following requirements prior to receipt of the study product:

- Abstain from taking medications, recreational drugs or engaging in alcohol intake 48 hours prior to receipt of the study product and through Day 15.
- Abstain from tobacco use from the time of screening through Day 15.
- Fasting 8 or more hours prior to receipt of study product.

## 6.2 Enrollment/Baseline (Day 1): Clinic Visit 02

Eligible subjects will be asked to return to the Clinical Research Unit (CRU) having fasted for 8 or more hours.

### *General.*

- Review inclusion/exclusion criteria (including assessment of time of last oral food intake).
- Absence of medications in the past 48 hours will be confirmed.
- A brief interim medical history will be taken.
- A routine physical examination that assesses general appearance and the following areas/systems, including skin, lymph nodes, HEENT, neck, respiratory, cardiovascular, pulmonary, abdomen, extremities, musculoskeletal, and neurological will be performed by a clinician licensed to make diagnoses.
- Vital signs including oral temperature, blood pressure, and pulse will be obtained.
- A heparin lock will be inserted, blood will be drawn (10 mL) for baseline PK and (15 mL) for safety labs (hemoglobin, white blood cell count, including neutrophil and eosinophil counts, platelet count, prothrombin time, partial thromboplastin time, creatinine, Na, K, CL, CO2, urea nitrogen, ALT, AST, total bilirubin).
- Collect urine sample for urine dipstick for protein and glucose and PK baseline.
- **Randomization.** Randomized treatment assignments will be generated by a statistician at The EMMES Corporation, the statistical and data coordinating center (SDCC) for this study. Subjects will be registered using a web-based application developed by The EMMES Corporation. Upon entry of demographic data and confirmation of eligibility for the trial, the subject will be enrolled. After successful enrollment, a treatment assignment number will be displayed on the Enrollment Confirmation screen. The treatment assignment number is referenced against a confidential randomization list provided to the designated unblinded study personnel on-site to determine the study assignment. The EMMES Corporation will monitor the implementation of this process.

### *Administration of Study Medication (drug/placebo).*

A blinded study nurse will administer a single oral dose of coded oxfendazole/placebo to the subject. Escalating dose levels of 0.5, 1, 3, 7.5, 15, 30, and 60 mg/kg will be evaluated sequentially.

- Subjects will remain fasting for two hours after the administration of drug/placebo.
- Lunch and dinner will be provided. Subjects will be allowed to eat snacks but will be asked to avoid drinking grapefruit juice and excessive (>2 cups) coffee.
- 10 mL of blood for oxfendazole and metabolites will be drawn at at baseline ( prior to product administration), 1, 2, 4, 6, 8, 10, and 12 hours (all times have a window of +/- 15 minutes except the 10 and 12 hour samples which have a window of +/- 30 minutes- it is critical to record the exact time of blood draw).

- Urine will be collected (prior to product administration) and for the first 24 hours following drug administration. Following drug administration, urine for oxfendazole, metabolites will be collected for 0-4, 4-8, 8-12, and subjects will be sent home with a 24 hour urine container to collect all urine between 12-24 hours. A urine creatinine value will be tested on the 12-24 hours sample and used to calculate creatinine clearance.
- Assess adverse events throughout the day and prior to discharge from the CRU.
- Assess for AEs and SAEs
- Counsel on need to avoid alcohol, drugs, tobacco and medications throughout the study.

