During the screening process written informed consent will be obtained prior to any study activities. A complete medical history will be obtained including review of medications, supplements and vitamins. Vital signs including oral temperature, blood pressure, pulse, height, weight and an EKG will be performed and a routine physical exam will be performed by a licensed clinician. Laboratory tests for hemoglobin, white blood cell count with neutrophil and eosinophil count, platelet count, creatinine, alanine aminotransferase (ALT), aspartate aminotransferase (AST), total bilirubin, random glucose, urine dipstick for protein and glucose, hepatitis B surface antigen, hepatitis C antibody, and human immunodeficiency virus serology (HIV) will be conducted. Eligible subjects will be invited to join the study. They will be advised to

abstain from drug or alcohol use for the 48 hours prior to return on Day 1 and to avoid tobacco use from the day of screening through the end of the study.

On study Day 1, a review of the inclusion/exclusion criteria will be conducted with subjects. A brief interim medical history will be taken and review of medication history since screening visit. Vital signs, including oral temperature, blood pressure, and pulse will be obtained. A targeted physical exam will be performed by a licensed clinician. Blood will be drawn for baseline PK and safety laboratory tests (hemoglobin, white blood cell count with neutrophil and eosinophil count, platelet count, creatinine, Na, K, Cl, CO2, urea nitrogen, alanine aminotransferase (ALT), aspartate aminotransferase (AST), prothrombin time and partial thromboplastin time, total bilirubin, and urine dipstick for protein and glucose) and a spot urine sample will be obtained for PK baseline.

Volunteers will be randomized using the EMMES web-based application to receive a single oral dose of oxfendazole or placebo. The designated unblinded pharmacist will prepare the study product according to the treatment assignment for each subject.

Subjects will be administered a single oral dose of coded oxfendazole/placebo by a blinded study nurse or investigator. Subjects will be fasting for 8 hours prior to, and for two hours after, the administration of drug/placebo. On day of drug administration, lunch and dinner will be provided. Monitoring will start immediately after dosing and will continue for 2 weeks.

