On Day 1, subjects will be interviewed briefly to monitor for AEs and SAEs. Blood for oxfendazole and metabolites will be drawn at 0 (product administration), 1, 2, 4, 6, 8, 10, and 12 hours. Urine for oxfendazole and metabolites will be collected for 0-4, 4-8, 8-12, and subjects will be sent home with a 24 hour urine container to collect all urine between 12-24 hours. After 12 hours, the subjects will be allowed to return home. Subjects will be counseled to avoid drug, alcohol and tobacco use through the end of the study (day 15).

On Day 2, subjects will be interviewed briefly to review for concomitant medications, and any AEs or SAEs since the last visit. Vital signs, including oral temperature, blood pressure, and pulse will be obtained. A targeted physical exam will be performed if indicated by symptoms. Blood for oxfendazole and metabolites will be collected between 24-32 hours, and urine for oxfendazole and metabolites will be collected for the time frame 12–24 hours. A urine creatinine value will be tested on the 12-24 hours sample and used to calculate creatinine clearance.

On Day 3, subjects will be interviewed briefly to review for concomitant medications, and any AEs or SAEs since the last visit. Vital signs, including oral temperature, blood pressure, and pulse will be obtained. A targeted physical exam will be performed if indicated by symptoms. Blood for oxfendazole and metabolites will be collected at a time point between 48-60 hours, and a spot urine for oxfendazole and metabolites will be collected between 48-60 hours. Blood for safety laboratories (hemoglobin, white blood cell count with neutrophil and eosinophil count, platelet count, creatinine, Na, K, Cl, CO2, urea nitrogen, alanine aminotransferase (ALT),

aspartate aminotransferase (AST), prothrombin time and partial thromboplastin time, total bilirubin) will be obtained for the two sentinel subjects only.

[figure not shown]

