### **6.3 Follow-up (Days 2 – 8): Visits 03 through 07**

#### **Clinic Visit 03, Day 2**

- Vital signs including oral temperature, blood pressure, and pulse will be obtained.
- A targeted physical exam may be performed, if indicated.
- Review concomitant medications
- Review for AEs and SAEs
- Counsel on need to avoid alcohol, drugs, tobacco and medications throughout the study.
- 10 mL of blood for oxfendazole and metabolites will be drawn at 24 (+ 8) hours.
- Spot urine for oxfendazole, metabolites will be collected at 24 (+8) hours.

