## **8.5 Halting Rules**

Two sentinel subjects (1 study drug and 1 placebo) will be dosed and monitored 48 hours for adverse events prior to enrolling the remaining subjects in each cohort. If no drug-related SAE or grade 3 study drug related laboratory AE occurs in the sentinel subjects after 48 hours of observation, the remainder of the cohort may proceed with dosing.

An SRC composed of the Protocol Principal Investigator and Independent Safety Monitor will review blinded safety data for each completed cohort. Each new cohort will be dosed only after the 2-week safety data for the preceding group have been reviewed for the following events:

- The SRC will evaluate the safety data from each dose group and will allow continuation if there are no product related grade 3 AEs or if there are fewer than two product related grade 2 AEs identified.

Enrollment, dosing and study procedures will be halted for SMC review/recommendation if any of the following are reported:

- Any death occurring after administration of study drug through the subject's last study visit that was not the result of trauma or accident, regardless of relatedness to study product.
- Any subject experiences laryngospasm, bronchospasm, or anaphylaxis within 24 hours after administration of study product.
- Any subject experiences a study drug-related Stevens Johnson Syndrome.
- Two or more subjects experience generalized urticaria within 72 hours after administration of study product.
- Any subject experiences a study drug-related SAE from the time of receipt of study drug through the subject's last study visit.
- Any subject develops new EKG changes that are deemed significant by a reviewing cardiologist.
- Any subject develops grade 3 laboratory abnormalities deemed related to the study drug.
- The SRC members are not unanimous in their agreement to proceed to the next dosing group or cannot assess or do not unanimously agree on the relatedness of the adverse event to the study product.

If any of the halting rules are met following any subject receipt of study drug, the study will not continue with the remaining enrollments without a review by and recommendation from the SMC to proceed.

DMID retains the authority to suspend additional enrollment and study interventions/administration of study product during the entire study, as applicable.

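### No vital signs are scheduled between the dose and Day 2, so symptom-free pulse, blood pressure or temperature changes on the day of first human exposure can be missed

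*Protocol*

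**What the plan says.** **Before the dose.** Protocol Section 6.2, in its general Day 1 list, states "Vital signs including oral temperature, blood pressure, and pulse will be obtained". The item comes ahead of the baseline blood draw, randomization and administration. Section 4 has the same order: "Vital signs, including oral temperature, blood pressure, and pulse will be obtained. A targeted physical exam will be performed by a licensed clinician", then baseline blood, randomization and dosing.

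**After the dose.** The administration list in Section 6.2 covers fasting, meals, pharmacokinetic blood, urine, adverse event assessment and counselling. Its safety item is "Assess adverse events throughout the day and prior to discharge from the CRU". Section 4 describes the check as an interview: "On Day 1, subjects will be interviewed briefly to monitor for AEs and SAEs". It also says "Monitoring will start immediately after dosing and will continue for 2 weeks", without naming a measurement or a time.

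**Length of stay and next contact.** Section 4: "After 12 hours, the subjects will be allowed to return home". For Visit 03 on Day 2, Section 6.3 lists vital signs and says "10 mL of blood for oxfendazole and metabolites will be drawn at 24 (+ 8) hours".

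**General rules.** Sections 7.1 and 8.2.2 call for vital signs at every visit and give no times within a visit. Appendix A has one untimed mark for Day 1, and the footnote to that row concerns the grading scale, not timing.

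**The concern.** This is the first use of oxfendazole in humans (Sections 2.1 and 2.3.1), at seven escalating dose levels. The protocol samples plasma most densely in the first 12 hours but attaches no vital sign to any of those draws. The first EKG after dosing is on Day 4, so no cardiovascular measurement of any kind is scheduled on Day 1 after the dose.

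Section 8.2.1 counts an unfavorable sign as an adverse event. Appendix B grades fever, pulse and blood pressure on numerical cut-offs: a pulse of 120 or a systolic pressure of 82 mmHg is Grade 2 by the number alone. A subject who feels well cannot report such a reading at interview.

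Two uses of the data are exposed:

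- the primary endpoint in Section 3.2, which counts related adverse events from the dose to 14 days;
- the cohort review in Section 8.5, where the Safety Review Committee (SRC) weighs product-related Grade 3 and Grade 2 events before the next dose level.

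**Working it through.** **1. Count the scheduled readings.**

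| Item | Source | Value |
|---|---|---|
| Vital-sign sets before the dose, Day 1 | Protocol 4, 6.2 | 1 |
| Pharmacokinetic draws after the dose, Day 1 (1, 2, 4, 6, 8, 10, 12 h) | Protocol 6.2 | 7 |
| Of these, with a scheduled vital sign | Protocol 4, 6.2 | 0 |
| Time on site after the dose | Protocol 4 | 12 h |
| Visit 03 draw | Protocol 4, 6.3 | 24 to 32 h |

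SAP Section 3.1 gives 14 plasma time points including baseline, so 13 follow the dose and 7 of the 13 fall in the first 12 hours.

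**2. Length of the gap.** Visit 03 vital signs have no clock time of their own. If they are taken with the Visit 03 draw, the gap is 24 to 32 h: 12 h on site plus 24 − 12 = 12 h to 32 − 12 = 20 h at home.

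**3. What the Appendix A mark shows.** The Day 1 mark for pharmacokinetic blood is also single, yet it stands for eight draws (one baseline and seven later). A single mark therefore does not show how often vital signs are taken. The finding rests on the order of procedures in Sections 4 and 6.2.

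**4. Which rules a missed reading could reach.**

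- *Primary endpoint, Section 3.2:* any related adverse event within 14 days, so yes.
- *SRC review, Section 8.5:* related Grade 3 events, or two or more related Grade 2 events, so yes. The Grade 2 part matters on its own only if both conditions in that sentence, which are joined by 'or', must be met for continuation.
- *Sentinel criterion, Sections 4 and 8.5:* a drug-related serious event or a drug-related Grade 3 laboratory event. A graded pulse, blood pressure or temperature is not a laboratory event, so no.

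**5. The protocol's own detection figure.** Table 4 gives 80% for at least one event with N = 8 and a true rate of 18%: 1 − (1 − 0.18)^8 = 0.796, which reproduces. The bound with no events observed is 1 − 0.05^(1/8) = 0.312, against 31% stated. Both presume that an event that occurs is recorded.

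**6. Illustration only.** Suppose a class of transient vital-sign events has a true rate of 18% and a share s is recorded. Neither the rate for such events nor s is in the documents. Then P(at least one) = 1 − (1 − 0.18s)^8, and the true rate excluded by no recorded events is 0.312/s.

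| Assumed s | P(at least one recorded) | True rate excluded if none recorded |
|---|---|---|
| 1 | 80% | 31% |
| 0.75 | 69% | 42% |
| 0.5 | 53% | 62% |
| 0.25 | 31% | no bound below 100% |

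This shows how Table 4 depends on ascertainment. It does not estimate the loss in this trial.

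**The case against.** **A reading is permitted, even if not scheduled.** Staff are present for 12 hours, adverse events are assessed throughout the day, Section 7.1 allows a targeted examination at any visit, and the Manual of Procedures, which is not among the documents, may add readings. This stands: the supportable statement is that no reading is scheduled, not that none will be taken. But nothing cited requires one, and a symptom-free subject gives no prompt for one.

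**The preclinical targets lie elsewhere.** Section 2.1.1.4 directs safety monitoring to bone marrow and liver, and Section 2.1.1.5 reports no vital-sign or EKG changes in dogs after single doses up to 100 mg/kg. This is fair context and lowers the prior concern. It does not replace measurement in the first human exposure.

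**Stronger readings that the documents do not support:**

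- *That the sentinel decision is compromised.* The formal criterion does not use vital-sign grades, and the 48-hour observation includes the Day 2 set.
- *That the halting rule "Any subject experiences laryngospasm, bronchospasm, or anaphylaxis within 24 hours after administration of study product" cannot work.* These are clinically overt events, and routine readings are not the only way to find them.
- *That vital signs are limited to one set per visit.* Sections 7.1 and 8.2.2 say at each visit and give no number.
- *That detection is nil instead of 80%.* It is nil only for an event defined as symptom-free, over before Day 2 and never met by an ad hoc reading. The Table 4 figure is general binomial arithmetic, not a claim about transient vital signs.

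**Conclusion.** The point holds as a gap in scheduled measurement. As written, the schedule has 0 vital-sign readings at 7 attended post-dose contacts on Day 1, and the first later set is about 24 to 32 h after the dose. Symptom-free changes that resolve in between can be missed from the primary related-event rate and from the SRC's Grade 2/3 review. For the primary rate the error can only be downward. The plan also leaves unclear what the monitoring that starts at dosing consists of.

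The conclusion rests on three assumptions: that the order of items in Sections 4 and 6.2 is the intended order of procedures; that Day 2 vital signs accompany the Day 2 draw; and that the Manual of Procedures adds no Day 1 readings. It also takes the Section 3.2 endpoint, which counts all grades. Of the measures listed in Section 10.1, the two that count severe events would be touched only by Grade 3 readings.

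The size of the loss cannot be computed, because the documents give neither a rate of transient vital-sign events nor a share recorded. Readings not taken on Day 1 cannot be recovered at analysis.

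**What to change.** Reconcile the Day 1 text of Section 4, both Day 1 lists in Section 6.2 and the Day 1 column of Appendix A, so that post-dose monitoring includes scheduled vital signs during the 12-hour stay, at contacts that already take place. The sponsor's medical monitor should set the times; this review proposes none. If the Manual of Procedures already schedules such readings, bring them into the protocol. State that the readings are graded under Appendix B against the pre-dose value where a grade depends on baseline, and that they go into the adverse event data and the SRC's cohort review. Say how several readings in one subject count toward the event rate.

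The cost is one amendment, one eCRF page and, as an estimate not taken from the documents, a few minutes of existing staff time per reading. No visit is added. More readings will also produce some incidental low-grade events: eligibility admits a pulse above 50, while Appendix B lists 50 to 54 as Grade 1 bradycardia. The placebo subjects (2 per cohort, up to 14 in all) give some background against which to read these.
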